7.0 DEVICE DESCRIPTION

7.1 TrueTear Investigational Device

The TrueTear device delivers small electrical currents to the inner cavity of the nose, activating nerves that stimulate the body's natural tear production system.

The device consists of four distinct parts (Figure 1):

1. A reusable Base Unit which produces the electrical stimulation waveform.
2. A disposable Tip that inserts into the nasal cavity and stimulates the target intranasal tissue.
3. A reusable Cover to protect the Tip.
4. A Charger which recharges the battery inside the Base Unit.

Base Unit with Cover

Base Unit with Disposable Tips (Front and Back)

TrueTear System

Figure 1 The TrueTear System Components

7.1.1 Base Unit

When activated, the Base Unit provides electrical pulses to the Tip. The strength of these pulses is controlled by two buttons, with five different intensity levels available, indicated by the number of illuminated LEDs on the Base Unit. The device internally records the time and duration of device use.

7.1.2 Disposable Tip

The disposable Tip is specially designed to allow the participant to easily apply stimulation to the target areas within the nose. The Tip attaches to the Base Unit and contains hydrogel (similar to the material used in contact lenses) that contacts the inside of the nose to provide stimulation. Each tip may be used up to 24 hours. After 24 hours, the used tip should be discarded and a fresh tip should be attached. A separate Cover can be used to protect the Tip and Base Unit when the device is not in use.

7.1.3 Cover

The Cover may be placed over the top of the Tip attached to the Base Unit for protection in between uses.

7.1.4 Charger

The Base Unit may be recharged by removing the Tip and placing the Base Unit onto the Charger. Charging typically takes under 4 hours, and a green LED indicates that the process has completed.

7.2 TrueTear Accountability

Each Base Unit and Charger have unique serial numbers. The serial numbers of the Base Unit/Charger used by each participant will be recorded on the appropriate case report form and device accountability log. The disposable Tip is provided in a sealed pouch, which is labeled with a lot number and expiration date. The lot number of the Tips provided to the participant will also be recorded on the appropriate case report forms and on the device accountability log. Tips should not be used beyond the expiration date provided on the pouch.

7.3 Control Description - Thermalon Dry Eye Compress

As described on the label, the Thermalon Dry Eye Compress [REDACTED]
[REDACTED]
[REDACTED]

[REDACTED]

7.4 Other Study Supplies

The following will be provided by the Investigator:

- Urine pregnancy test kits
- Schirmer test strips
- Weck-Cel eye spears
- Proparacaine
- Liquid sodium fluorescein
- Calibrated 1-10 µL pipette and sterile pipette tips

8.0 STUDY METHODS AND PROCEDURES

8.1 Participant Entry Procedures

8.1.1 Overview

Participants as defined by the criteria in section 5.2, 5.3, and 5.4 will be considered for entry into this study.

8.1.2 Informed Consent

Prior to a participant's participation in the trial (i.e., prior to study-related procedures), the study will be discussed with each potential participant and participants wishing to participate should give written informed consent using an IRB approved informed consent form (ICF). The ICF should be the most recent version that has received approval by a properly constituted IRB.

[REDACTED]

[REDACTED]

- [REDACTED]
- [REDACTED]
- [REDACTED]
- [REDACTED]

[REDACTED]

- [REDACTED]
- [REDACTED]

[REDACTED]

- [REDACTED]
- [REDACTED]
- [REDACTED]
- [REDACTED]
- [REDACTED]
- [REDACTED]

8.1.4 Procedures for Final Study Entry

Participants should meet all inclusion and none of the exclusion criteria.

8.1.5 Methods for Assignment to Application Groups

At the Screening Visit, participants who provide written informed consent will be assigned a unique 5-digit screening number, [REDACTED]. Screening numbers should be assigned in ascending consecutive order. Participants who meet all of the eligibility criteria will be scheduled to return for Visit 2 (Day 0).

At Visit 2 (Day 0), participants who meet all eligibility criteria will be randomized to one of two treatment groups (TrueTear or Thermalon Dry Eye Compress control) in a 1:1 ratio. At Visit 2 (Day 0), participants will be randomized in sequential order. The randomization number will be recorded on the CRF/source document.

8.2 Masking

Because the two devices are dissimilar and administered in very different ways, it will not be possible to mask the participant or the Investigator to the intervention assignment. As a means of minimizing bias where feasible, de-identified videos from the Tearscope assessment (lipid layer thickness) will be graded using the Guillon scale in a masked fashion.

8.3 Participant Training, Dispensing and Home Use of TrueTear

At Visit 2 (Day 0), participants randomized to the TrueTear application group will be provided a TrueTear device and disposable tips to take home with them and use daily. Participants will be instructed to use the device as described in the Patient Guide. They will receive training to perform intranasal neurostimulation and will receive a copy of the Patient Guide.

For the device application, participants will be told to turn on the unit by holding down the + button for approximately two seconds. There are five stimulation intensity levels and participants may adjust the level by pressing the + or – buttons to obtain a gentle tingling sensation. They will be instructed to fully insert the tips of the TrueTear into both nostrils simultaneously towards the top and front of the nose (as in Figure 2). Participants will be told they can cease stimulation by holding down the – button for approximately two seconds on the base unit or by withdrawing the tips from the nostrils. Participants will be instructed to replace the Tips with a new one if they do not feel any sensation.

For the initial in-office device application at Visit 2 (Day 0), each participant will be told that the application will take place for approximately eight minutes and that the entire procedure will occur while the participant is seated and positioned in a slit lamp to allow for simultaneous viewing of meibomian gland activity in the lower lid and for collection of lid and tear film temperature data.

At Visit 3 (Day 7), prior to in-office application and evaluation of tear secretion, trained clinical personnel will review procedures for the proper use of the device (e.g., correct positioning intranasally, frequency and duration of use, daily replacement and disposal of tips, etc.) with participants. As the device internally records the frequency and duration of device use, study staff may review this information with participants. Participants will be told that the in-office application of TrueTear at this visit should last for approximately three minutes.

Figure 2 Use of TrueTear

(L) Starting position and (R) Correct application position by inserting the disposable tips fully into the nasal cavity and to the front of the nose.

Note: Sponsor representatives may be present at visits to assist in training participants on the use of the device.

8.4 Participant Training, Dispensing and Home Use of Thermalon Dry Eye Compress

At Visit 2 (Day 0), participants randomized to the Thermalon Dry Eye Compress application group will be provided a Thermalon Dry Eye Compress device to take home with them and use daily. Participants will be trained to follow the instructions for proper use and storage as described on the package insert or [REDACTED]. The following additional points will be noted:

- Between study visits, participants will be asked to use the moist heat compress daily as described on the package insert [REDACTED]
- If participants wish to wash their compress, instructions can be found on the package insert or [REDACTED]
- Participants will be reminded to fill out a diary to record daily use of the moist heat compress throughout the study duration.
- Participants will be asked to return the moist heat compress at the end of the study.

8.5 Concurrent Therapies

The use of any concurrent medication, prescription or OTC, is to be recorded on the participant's CRF along with the reason the medication was taken. Concomitant medications that are considered necessary for the participant's welfare, but will not interfere with study assessments and evaluations, will be allowed during the study at the Investigator's discretion.

Concurrent enrollment in another investigational drug or device study is not permitted.

[REDACTED]

- [REDACTED]
- [REDACTED]
- [REDACTED]
- [REDACTED]
- [REDACTED]
- [REDACTED]
- [REDACTED]
- [REDACTED]
- [REDACTED]
- [REDACTED]
- [REDACTED]
- [REDACTED]
- [REDACTED]
- [REDACTED]

[REDACTED]

[REDACTED]

[REDACTED]

[REDACTED]

[REDACTED]

- [REDACTED]
- [REDACTED]
- [REDACTED]
- [REDACTED]

■ [REDACTED]	[REDACTED]

[REDACTED]

[REDACTED]

[REDACTED]

[REDACTED]

8.8 Completed Participants

A completed participant is one who has not been discontinued from the study and has successfully completed Day 30.

8.9 Study Termination

The study may be stopped at any time by the Investigator, the Sponsor, and/or [REDACTED] with appropriate notification.

8.10 Study Duration

An individual participant's participation will involve up to five visits over approximately a 44 day period.

8.11 Monitoring and Quality Assurance

8.11.1 Study Monitoring

Allergan personnel (or designees) will monitor this study in a manner consistent with applicable health authority regulations and the procedures adopted by the SOPs of Allergan. Prior to the start of the study, member(s) of [REDACTED] (or designees) will review the protocol, CRFs, regulatory obligations, and other material or equipment relevant to the conduct of the study with the Principal Investigator/Sub-Investigator(s) and pertinent study staff.

Monitoring visits will occur as necessary during the course of the investigation to verify:

- The rights and well-being of participants are protected
- The conduct of the investigation is in compliance with the currently approved protocol/amendment, GCP and IRB/IEC requirements
- The integrity of the data
- Study device accountability

- Adequate study documentation

During the course of the study, if the Sponsor (or designee) determines that the Investigator is non-compliant with the study plan and/or applicable regulatory requirements, the Sponsor (or designee) will take written action to correct the non-compliance and to secure compliance. In addition, the Sponsor (or designee) may terminate the Investigator's participation in the study if appropriate, or if the Investigator remains non-compliant despite the Sponsor's actions. This termination will be documented in a memo or follow-up letter to the Principal Investigator.

8.11.2 Recording of Data

Participant data recorded on CRFs during the study will be documented in an anonymous fashion. The participant will only be identified by the participant number. If, as an exception, it is necessary for safety or regulatory reasons to identify the participant, the Sponsor or its representatives, and the Investigator, are bound to keep this information confidential.

9.0 ADVERSE EVENTS

An AE is defined as any unfavorable and unintended sign (including an abnormal laboratory finding) symptom, or disease temporally associated with the use of an investigational product but not necessarily related to the investigational product. An AE may also be called a complication. The capture of AEs will begin with the participant's entry into the study.

9.1 Adverse Event Recording

All AEs spontaneously reported by the participant and/or in response to an open question from study personnel or revealed by observation, physical examination or other diagnostic procedures will be recorded on the appropriate pages of the CRF. Any clinically relevant deterioration in clinical finding is considered an AE and should be recorded. When possible, signs and symptoms indicating a common underlying pathology should be noted as one comprehensive event.

9.2 Adverse Event Evaluation

The Investigator should evaluate if each AE is serious, related to the applicable study device and anticipated using the following definitions.

A serious adverse event (SAE) is defined as any untoward medical occurrence that:

- It results in death (i.e., the AE actually causes or leads to death);
- It is life threatening (i.e., the AE places the participant at immediate risk of death);
- It requires or prolongs inpatient hospitalization. If a participant is hospitalized to undergo a medical or surgical procedure as a result of an AE, the event responsible for the procedure, not the procedure itself, should be recorded as the event. For example, if a participant is hospitalized to undergo coronary bypass surgery, the

heart condition that necessitated the bypass should be recorded. Hospitalizations for diagnostic or elective surgical procedures or hospitalizations required to allow outcome measurement for the study should not be recorded as SAEs:

- It results in persistent or significant disability/incapacity (i.e., the AE results in substantial disruption of the participant’s ability to conduct normal life functions);
- It results in a congenital anomaly/birth defect in a neonate/infant born to a mother exposed to the investigational device;
- It is considered a significant medical event by the Investigator based on medical judgment (e.g. may jeopardize the participant or may require medical/surgical intervention to prevent one of the outcomes listed above);
- It is considered sight-threatening by the Investigator.

9.3 Relationship of the AE to the investigational device

Definite	A clear-cut causal relationship with the study device and no other possible cause
Probable	A causal relationship with the study device is likely although alternate etiologies are also possible
Possible	A causal relationship with study device is not definite, alternate etiologies are also possible
Not related	The AE has no causal relationship to study device and/or there is evidence of alternative etiology such as concurrent medication or illness.
Not applicable	The participant has not been exposed to the study device.

The AE will be determined to be device related, making it an adverse device effect (ADE), if it is identified to have had a definite, probable or possible causal relationship to the study device.

An AE is unanticipated if the nature, severity, or frequency of the event is not consistent with either the known or foreseeable risk of AEs associated with the procedures involved in the research that are described in (a) the protocol-related documents, such as the IRB-approved research protocol, user manuals and the current IRB-approved informed consent document, and (b) other relevant sources of information such as product labeling and package inserts; or the expected natural progression of any underlying disease, disorder, or condition of the participant(s) experiencing the AE and the participant’s predisposing risk factor profile for the AE.

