9.5 Adverse Event Reporting

All AEs that occur during the course of the study should be reported on the Adverse Event CRF. The Investigator should determine the intensity of the event.

Mild	Awareness of sign or symptom, but easily tolerated
Moderate	Discomfort enough to cause interference with normal daily activities
Severe	Inability to perform normal daily activities

[figure not shown]
All SAEs and adverse device effects (ADEs) should be reported by the Investigator to [REDACTED] and the Sponsor in writing within 24 hours from the point in time when the Investigator becomes aware of the event.

[figure not shown]
It is the responsibility of the Investigator to promptly notify the Institutional Review Board (IRB) of all unanticipated SAEs and unanticipated problems, per the IRBs reporting requirements.

Throughout the course of the proposed study, all efforts will be made to remain alert to possible adverse experiences or untoward findings. If adverse experiences occur, the first concern will be the safety and welfare of the participant. Appropriate medical intervention will be made.

[REDACTED] and the Sponsor will immediately conduct an evaluation of any unanticipated adverse device effect. The results of the evaluation will be reported to the IRB within 10 days of [REDACTED] and/or the Sponsor becoming aware of the event. If it is determined by [REDACTED] and the Sponsor to present an unreasonable risk to study participants, all investigations or parts of the investigation presenting that risk will be terminated as soon as possible. Termination will occur not later than five working days after [REDACTED] and the Sponsor makes this determination, and not later than 15 working days after first receiving notice of the event. [REDACTED] and the Sponsor will not resume an investigation terminated under these conditions without an additional IRB approval.

Contact information for reporting Serious Adverse Events:

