9.6 Anticipated Adverse Events

The following is a list of potential AEs associated with the use of the device:

- Nasal discomfort or pain
- Epistaxis
- Excessive sneezing
- Nasal irritation, paresthesia or numbness post-stimulation
- Nasal infection, abrasion or inflammation
- Skin irritation or hypersensitivity
- Headache (e.g., tension, migraine, etc.)
- Facial pain
- Excessive salivation
- Sensation of teeth vibrating
- Excessive rhinorrhea
- Temporary aggravation of nasal allergies
- Allergic reaction to contact materials

As described on the Thermalon Dry Eye Compress label, the following potential AE associated with the use of Thermalon Dry Eye Compress may occur:

- Blurry vision

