10.1 ADVERSE EVENTS

Adverse events will be coded by system organ class and preferred term using the *Medical Dictionary for Regulatory Activities*, version 20.1 or newer.

An AE will be considered a treatment-emergent adverse event (TEAE) if it was present one or after the first application of study treatment or was present before the date of the first application of study treatment and increased in severity or became serious on or after the first application of study treatment.

An AE will be considered a treatment-emergent serious AEs (TESAE) if it is a TEAE that additionally meets any SAE criteria.

The number and percentage of patients reporting TEAEs and treatment-related TEAEs in each treatment group will be tabulated by system organ class and preferred term, separately. If more than 1 AE is coded to the same preferred term for the same patient, the patient will be counted only once for that preferred term using the greatest severity.

A summary table will be provided for subjects with TEAE, TESAE, death and subjects with TEAEs leading to discontinuation if 5 or more participants reported such events. A subject listing of all AEs will be presented.

11.0 **INTERIM ANALYSIS**

No interim analysis is planned for this study.

12.0 **DETERMINATION OF SAMPLE SIZE**

As this is a proof of concept study, no formal calculation of sample size was conducted. Approximately 70 participants will be enrolled to achieve approximately 60 completed.

13.0 **STATISTICAL SOFTWARE**

Statistical analyses will be performed using version [REDACTED]
[REDACTED]

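### Protocol 9.3 lets evidence of another cause alone make an adverse event 'Not related', so an event with a plausible device role can be graded on either side of the ADE boundary

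*Protocol*

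**What the plan says.** Protocol 9.3 has four causality grades for exposed participants, plus *Not applicable* for those not exposed. The lowest of the four, *Not related*, is worded as follows: "The AE has no causal relationship to study device and/or there is evidence of alternative etiology such as concurrent medication or illness".

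Two of the three higher grades also leave room for other causes. The wording for *Probable* is: "A causal relationship with the study device is likely although alternate etiologies are also possible". *Possible* asks for less certainty about the device and makes the same allowance: "A causal relationship with study device is not definite, alternate etiologies are also possible". Only the top grade, *Definite*, shuts other causes out, by demanding the following: "A clear-cut causal relationship with the study device and no other possible cause".

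The section then turns grades into a classification. An event becomes an ADE on this condition: "if it is identified to have had a definite, probable or possible causal relationship to the study device".

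Three other places depend on the grade or bear on it:

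- Protocol 9.5 sets a 24-hour deadline for written reports that reach the Sponsor. The sentence opens: "All SAEs and adverse device effects (ADEs) should be reported by the Investigator to".
- Protocol 9.6 lists the risks expected with TrueTear. One entry is "Temporary aggravation of nasal allergies"; another is headache, with tension and migraine types given as examples.
- SAP 10.1 plans these patient counts: "TEAEs and treatment-related TEAEs in each treatment group will be tabulated by system organ class and preferred term". It does not say which of the 9.3 grades count as treatment-related.

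Protocol 8.2 states that neither participant nor investigator can be masked.

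**The concern.** A causality scale should place each event in one grade, at least across the line that carries consequences. Here that line runs between *Possible* and *Not related*. The *Not related* definition does not ask whether the alternative cause is the likelier one, or whether the device also contributed. Evidence that another cause exists is enough.

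An event the investigator thinks was probably due to the device, in someone with a documented concurrent illness, can therefore be graded *Probable* or *Not related* with equal support from the text. Two investigators could grade the same event differently and both comply. The study may run at two sites, and the grader knows the assignment, so the discretion could also be used differently in the two arms.

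Comparing safety is part of the primary objective. For non-serious events the grade alone decides ADE status and 24-hour reporting. It is also the natural source for the only planned SAP summary that attributes events to treatment.

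**Working it through.** The plan states no figure on this point, so the check is mainly one of logic: cross whether a device role is plausible with whether there is evidence of another cause, and read off the 9.3 grades that each combination satisfies.

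| Device role plausible? | Evidence of another cause? | Grades satisfied as written | ADE? |
|---|---|---|---|
| Yes | No | *Definite* if clear-cut with nothing else possible; *Probable* or *Possible* if another cause is conceivable but not evidenced | Yes |
| Yes | Yes | *Probable* or *Possible*, and also *Not related* through its second limb | Yes or no |
| No | Yes | *Not related* | No |
| No | No | *Not related* through its first limb | No |

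Only the second row is ambiguous, and its ambiguity straddles the ADE boundary. *Definite* cannot overlap, because it excludes any other possible cause. *Possible* as worded also takes in *Probable*, but both are ADE grades, so that overlap has no consequence.

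**Can listed events fall in the second row?** Aggravation of a nasal allergy presupposes an existing allergy, which an investigator may cite as a concurrent illness. Headache in a participant with a history of migraine is similar. Protocol 9.6 lists both as potential effects of the device, so a device role is plausible by the protocol's own account.

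**Is there a rule that resolves it?** Protocol 9.1 to 9.6 contain no tie-break, no rule for aggravated conditions and no likelihood threshold. SAP 14.6 treats a missing causality as related and says nothing about overlapping grades.

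**Size of one reclassification.**

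- Input: approximately 70 participants, randomized 1:1 (Protocol 4.0, 5.1).
- Assumption: all are treated, so each arm of the Safety Population has 70 / 2 = 35.
- One participant whose only related event moves to *Not related* lowers that arm's treatment-related incidence by 1 / 35 = 0.0286, or about 2.9 percentage points.

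The documents give no expected rate of device-related events and no rate of concurrent illness, so the number of participants affected cannot be derived.

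**The case against.** **The wording differs in strength.** *Not related* needs evidence of another cause, while the ADE grades say only that other causes are possible. Under the label *Not related*, that evidence could naturally be read as evidence that something else caused the event. This narrows the overlap: not every *Probable* or *Possible* event also meets *Not related*. It does not remove it, because the text never says that the other cause must be the likelier or the sole one.

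**The ADE sentence is inclusive.** Any event identified as definite, probable or possible is an ADE, which might seem to settle the matter in favour of reporting. But that sentence acts on a grade already chosen. It does not tell the investigator which grade to choose.

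**Other safeguards exist.** This stands. SAP 10.1 tabulates all TEAEs by arm whatever the grade, which gives a randomized safety comparison without any causality judgement. All AEs are listed, and SAEs go to the Sponsor within 24 hours regardless of causality. Events are misattributed, not lost. Since the two examples are on the anticipated list, they would not ordinarily trigger the evaluation of unanticipated effects either.

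**Stronger readings go too far.** A reader might infer that every allergy aggravation meets *Not related*. It does not: a pre-existing allergy is the thing aggravated and need not be evidence of what aggravated it. A reader might extend the point to dry-eye worsening, or to blurry vision with the compress, because participants are enrolled with dry eye or MGD. The documents do not list dry-eye worsening as a device risk or call the enrolled disease a cause of blurry vision, so those examples are inference. A reader might also conclude that related counts are biased downwards by some stated amount. The text shows discretion; it does not show how often or in which direction it would be used.

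**Conclusion.** The point holds in a limited form. As written, 9.3 allows an event with both a plausible device role and an evidenced concurrent illness or medication to be graded as an ADE or as unrelated, and nothing in either document settles which. This is a stated rule that can misclassify events, so it is more than missing detail.

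The consequences are confined to ADE status and 24-hour reporting of non-serious events, and to the treatment-related TEAE table. The second rests on the assumption that the 9.3 grades feed that table. SAP 10.1 does not say so, and SAP 14.6 speaks only of a yes/no causality.

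The 2.9-point figure assumes 35 treated per arm and is the effect of a single reclassified participant, not an estimate of total error. The correction is worth making because it is cheap and safety is in the primary objective, but the main between-arm safety comparison does not depend on it.

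**What to change.** In Protocol 9.3:

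- Delete 'and/or' and define *Not related* as no reasonable possibility that the device caused or contributed to the event. An alternative etiology may be recorded as supporting evidence, but is neither sufficient nor required.
- State that aggravation of a pre-existing condition is graded at least *Possible* when a device contribution is plausible.

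Simply changing 'and/or' to 'and' would not work. An event with no device role and no identified cause (the last row of the table) would then have no grade.

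In SAP 10.1, state that *Definite*, *Probable* and *Possible* count as treatment-related, and align the yes/no language of SAP 14.6 with that mapping.

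The cost is a few sentences across the protocol and SAP, with matching instructions for completing the CRF. The downside is a slightly higher related-event count and a few more 24-hour ADE reports.

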10.0 PREGNANCY

Women of Childbearing Potential (WOCBP) include any females who have experienced menarche and who have not undergone successful surgical sterilization (hysterectomy, bilateral tubal ligation or bilateral oophorectomy) or are not postmenopausal at least 12 months since last menses. WOCBP will be required to use designated methods of birth control during the course of the study such as abstinence, sterile male partner, oral contraceptive pills, contraceptive patches, injectable contraception, vaginal rings, intrauterine contraception, or barrier methods. All women who are pregnant, nursing an infant, or planning a pregnancy during the duration of this study will be excluded from participation.

If a participant or Investigator suspects that the participant may be pregnant prior to study device administration, the study device should be withheld until the results of pregnancy testing are available. If pregnancy is confirmed, the participant should not administer the study device and should not be enrolled in the study.

If a female participant becomes pregnant during the study, the Investigator will notify Allergan immediately after the pregnancy is confirmed. The Investigator will (1) obtain a consent from the female participant for pregnancy follow-up and (2) follow the progress of the pregnancy to term. The Investigator must document the outcome of the pregnancy and provide a copy of the documentation to Allergan.

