13.3 REGULATORY STATUS

A previous version of the TrueTear (formerly known as the Oculeve Intranasal Lacrimal Neurostimulator) received [REDACTED]. It has been approved for marketing in Canada and Australia as well. The current version of TrueTear is an investigational device in the US.

The Thermalon Dry Eye Compress is legally sold by its manufacturer [REDACTED] [REDACTED] as a class I device in the USA and does not require premarket approval or notification.

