13.4 Labeling, Packaging, Storage, Accountability, and Return or Disposal of Study Device

All investigational devices will be clearly labeled "For Investigational Use Only." The distribution and return of all devices will be recorded. Used disposable tips should be discarded after use; unused disposable tips should be returned to the Sponsor at the conclusion of the study.

A device accountability log will be maintained by the site and will be filed in the Trial Master File.

13.5 Labeling, Packaging, Storage, Accountability, and Return or Disposal of Thermalon Dry Eye Compresses

Thermalon Dry Eye Compresses will be purchased commercially and will be dispensed to participants in commercial packaging with a study label. Participants will be referred to the package insert or [REDACTED] for product use and storage information. At the end of the study, participants will be asked to return their compress.

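### Does the protocol leave it unclear whether adverse events in the compress arm can be graded as related to treatment?

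*Protocol*

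**What the plan says.** Protocol 9.2 sets the task: "The Investigator should evaluate if each AE is serious, related to the applicable study device", using the definitions that follow. Protocol 9.3 then gives five levels (definite, probable, possible, not related, not applicable). Its heading speaks of the investigational device and its levels of the study device. The last level is explained as "The participant has not been exposed to the study device". The first three levels make an event an adverse device effect (ADE).

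The vocabulary elsewhere varies. The Synopsis lists TrueTear as the study device and the compress under controls. Section 7.1 is titled "TrueTear Investigational Device", and 13.3 states "The current version of TrueTear is an investigational device in the US". Section 13.4, "Labeling, Packaging, Storage, Accountability, and Return or Disposal of Study Device", is separate from 13.5 on compresses. Section 10.0, however, uses the term for any participant: "prior to study device administration, the study device should be withheld until the results of pregnancy testing are available".

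SAP 10.1 tabulates treatment-related treatment-emergent events (TEAEs) by arm without defining treatment-related. SAP 14.6 imputes yes when causality is missing for an event starting on or after first dose, and still carries a bracketed template note about a 3-point scale.

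**The concern.** If the study device means TrueTear alone, no compress participant is ever exposed to it, and every compress-arm event would be not applicable. The control column of the related-TEAE table would then be near zero because of coding, although 9.6 names blurry vision as a compress risk. If up to two sites read the scale differently, that column would mix two codings. Comparing safety is part of the primary objective, so a distorted by-arm table would matter. ADE status turns on the same term, and 9.5 attaches expedited reporting to it: "All SAEs and adverse device effects (ADEs) should be reported by the Investigator to" the sponsor within 24 hours. The SAP does not say how a not-applicable code is counted.

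**Working it through.** The documents give no event rates and no formal sample size calculation, so there is no figure to reproduce. The check compares the passages under the two readings and then sizes the worst case.

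**Which reading fits the text?**

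| Place | TrueTear-only reading | Assigned-product reading |
|---|---|---|
| Protocol 9.2, applicable device | The adjective has no work to do | Fits |
| Protocol 9.3 heading | Fits | Loose wording |
| Protocol 9.0, AE defined by use of an investigational product | Compress participants could hardly have an AE | Fits |
| Protocol 9.6, expected compress event | Listed to no purpose | Fits |
| Protocol 8.2, 8.4, 11.2, 13.3 | Conflicts: the compress is called a device | Fits |
| Synopsis, 7.1, 13.4/13.5 | Fits | Product description and accountability, not causality |
| SAP 5.2, Safety Population needs one device application | Would exclude the control arm | Fits |
| SAP 10.1, related TEAEs in each arm | Control column has no meaning | Fits |

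Section 9.2 gives the instruction, and 9.3 is the definition it points to. The device in 9.3 is therefore most naturally the applicable one from 9.2.

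**Does the not-applicable level need the narrow reading?** No. Section 9.0 states "The capture of AEs will begin with the" participant's entry into the study, while first application is at Visit 2 (Day 0). Events in that interval need a level of this kind in both arms. SAP 10.1 counts an event as treatment-emergent only if it is present, worsens or becomes serious from first application onward. On the assigned-product reading an event that begins after first application would not carry the code.

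**Does SAP 14.6 cause an error?** The template note is conditional on a 3-point scale. The protocol's scale has five levels, so the condition is not met. Imputing yes is the same as imputing related, which the protocol defines as definite, probable or possible. A recorded not-applicable code is a recorded value, so the rule for missing causality does not touch it.

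**Size on the narrow reading.** About 70 participants at 1:1 give 70/2 = 35 per arm. If *k* compress participants have a compress-caused event coded not applicable (*k* assumed), the control rate falls by *k*/35:

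- *k* = 1: 1/35 = 2.9 points
- *k* = 3: 3/35 = 8.6 points
- *k* = 5: 5/35 = 14.3 points

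A displayed 0/35 has an exact two-sided 95% upper limit of 1 − 0.025^(1/35) = 10.0%. The SAP plans only counts and percentages for adverse events, so this limit would not be reported. Nor is 0/35 assured, because a compress TEAE that started on or after first dose with blank causality would still count as related under SAP 14.6.

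On the assigned-product reading the shift is 0 for every *k*.

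**The case for a change.** The best case for acting is that investigators grade from the scale, and the scale does not name its reference product. Even within section 9, the list in 9.6 uses the device to mean TrueTear and then names the compress separately. A site reading 9.3 alone could go wrong, neither SAP 10.1 nor 14.6 would catch it, and the cure is only wording.

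Three parts of this stand. The terms are inconsistent, the template note should have been removed before approval, and it is not spelled out whether a related, non-serious compress event is an ADE for 24-hour reporting. The last point is narrow, because 9.5 sends all serious events to the sponsor within 24 hours whatever their cause, and 9.4 is worded for any device.

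What does not stand is the claim that the two sections give opposed instructions. One gives the instruction and the other supplies the scale. The case report form and the table specifications, where the reference product would be applied in practice, are separate documents and were not available, so their content cannot be counted for or against the plan.

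**Conclusion.** The concern does not hold as a fault in the analysis. Causality can be graded in both arms, and the by-arm table of related events is sound as a descriptive display. What remains is uneven terminology and leftover template text, which an analyst would handle correctly by using the protocol's own definition of related for each arm's product. The potential distortion of 2.9 points per affected participant needs both a reading that most of the documents contradict and event counts that are assumed. Even then, all TEAEs would still be tabulated by arm and every event listed, so a miscoded compress event would remain visible. The conclusion assumes that investigators follow 9.2 when they use the 9.3 scale and that the case report form does not say otherwise.
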